3.2 Post-study Access to Therapy

At the end of the treatment phase of the study, BMS will not continue to supply study drug to subjects/investigators unless BMS chooses to extend the study. The investigator should ensure that the subject receives appropriate standard of care to treat the condition under study. No exceptions to these criteria will be granted by the Sponsor.

3.3 Study Population

For entry into the study, the following criteria **MUST** be met prior to dosing on Day 1. No exceptions will be granted.

3.3.1 Inclusion Criteria

1) Signed Written Informed Consent

- a) The subject must sign the informed consent form prior to the performance of any study related procedures that are not considered part of standard of care.

2) Target Population

- a) Subjects must have histologic or cytologic confirmation of a solid malignancy that is advanced (metastatic and/or unresectable):
 - i. Dose Escalation (Part 1) Not applicable starting with Protocol Amendment 13 and all subsequent amendments.
 - i. All solid tumor histologies will be permitted during dose escalation, except for subjects with primary CNS tumors or with CNS metastases as the only site of active disease.
 - ii. Subjects must have received, and then progressed or been intolerant to, at least 1 standard treatment regimen in the advanced or metastatic setting, if such a therapy exists (except for subjects with MEL).
 - ii. Cohort Expansion (Part 1) Not applicable starting with Protocol Amendment 13 and all subsequent amendments.
 - i. The following 5 tumor types will be permitted during cohort expansion.
 1. NSCLC
 - a) Must have recurrent or PD during or after platinum doublet-based chemotherapy for advanced or metastatic disease *or* must have recurrent or PD within 6 months after completing platinum-based chemotherapy for local disease.
 - b) Subjects must have known epidermal growth factor receptor (EGFR) and anaplastic lymphoma kinase (ALK) status.

- c) Subjects with an activating EGFR mutation must have received an EGFR tyrosine kinase inhibitor.
 - d) Subjects with an ALK translocation must have received an ALK inhibitor.
2. MEL
- a) Must have received prior therapy with ipilimumab.
 - b) BRAF mutation status must be known, and if a BRAF mutation (V600E or V600K) is present, the subject must have received a RAF or a MEK inhibitor.
3. CRC
- a) Subjects must have phenotypes:
 - i. Microsatellite instability (MSI) stable (no alterations) or MSI low (only 1 alteration) with MSI expression detected by an accredited laboratory per local process. See [Section 5.3.1](#) or
 - ii. Deoxyribonucleic acid (DNA) mismatch repair gene proficient on tumor immunohistochemistry (IHC).
 - b) Known Kirsten Ras (KRAS) mutation status.
 - c) Prior therapy requirement:
 - i. Must have received at least 1 standard systemic therapy, such as fluoropyrimidine, oxaliplatin or irinotecan, bevacizumab, cetuximab or panitumumab (if KRAS wild type), or regorafenib.
 - or
 - ii. Subject refused standard therapy for the treatment of metastatic (Stage 4) or locally advanced disease. The subject's refusal must be documented.
4. SCCHN (oral cavity, pharynx, larynx)
- a) Must document HPV status and subtype, particularly HPV16 and HPV18.
 - b) Must have evidence of progression or recurrence within 6 months of last dose of platinum therapy.
 - c) Radiation therapy must have been completed at least 4 weeks prior to study drug administration.

5. HCC that is not amenable to surgical resection
 - a) Subjects must have PD, or been intolerant to, at least 1 line of therapy or refuse treatment with sorafenib.
 - b) Child-Pugh score of B (7 points or less and must not have encephalopathy) (see [Appendix 5](#)).
 - c) Subjects must have testing for hepatitis B surface antigen (HBsAg), hepatitis B surface antibody, hepatitis B core antibody, hepatitis B DNA polymerase chain reaction (PCR), hepatitis C antibody, hepatitis C ribonucleic acid (RNA) PCR.
 - d) Subjects with hepatitis B infection must have hepatitis B DNA viral load < 100 IU/mL and must be on anti-viral therapy per institutional guidelines.
 - e) Subjects with hepatitis B infection must not have co-infection with hepatitis C or hepatitis D (must obtain hepatitis D antibody testing).
 - f) Subjects must not have clinically significant ascites or clinically significant variceal bleeding.
6. The SCCHN Cohort Expansion (Part 2; completed) in squamous cell carcinoma of the head and neck (oral cavity, pharynx, larynx) Not applicable starting with Protocol Amendment 13 and all subsequent amendments.
 - a) Histologically confirmed, incurable, locally advanced, recurrent or metastatic SCCHN (oral cavity, pharynx, larynx), Stage 3/4 and not amenable to local therapy with curative intent (surgery or radiation therapy with or without chemotherapy).
 - b) Confirmation of tumor HPV status: Prior testing results are acceptable if known. If tumor HPV status is unknown, subjects must consent to allow their submitted archived tumor tissue sample in the form of block or unstained slides to be tested for confirmation of tumor HPV status.
 - c) Tumor progression or recurrence within 6 months of last dose of platinum therapy in the adjuvant (ie, with radiation after surgery), primary (ie, with radiation), recurrent, or metastatic setting. Clinical progression after platinum therapy is an allowable event for entry and is defined as progression of a lesion at least 10 mm in size that is amenable to caliper measurement (eg, superficial skin lesion as per RECIST v1.1) or a lesion that has been

visualized, photographically recorded with measurements, and shown to have progressed.

- d) Prior curative radiation therapy must have been completed at least 4 weeks prior to study drug administration. Prior focal palliative radiotherapy must have been completed at least 2 weeks before study drug administration.
- e) Subjects must consent to allow the acquisition of existing FFPE material for performance of correlative studies including (but not limited to) the analysis of PD-L1 expression by IHC (additional subjects may be enrolled if necessary to ensure an adequate number of higher PD-L1 expressers):
 - i. FFPE tissue may be in the form of either a block or unstained slides, but a fresh biopsy may be performed when a subject's prior archived tumor tissue has been exhausted;
 - ii. Tumor tissue must be confirmed as shipped to the central laboratory prior to subjects receiving study drug.
- ii. Subjects must have ≤ 5 prior treatment regimens. The following are not considered separate lines of treatment: addition of a compound to an ongoing regimen, restarting the same regimen after a drug holiday, or switching from IV to oral therapy.
- iii. The SCCHN Randomized Cohorts (Part 3 - enrollment closed)
 - 1. Histologically confirmed recurrent or metastatic SCCHN (oral cavity, pharynx, larynx), Stage 3/4 and not amenable to local therapy with curative intent (surgery or radiation therapy with or without chemotherapy).
 - 2. Documentation of p16-positive or p16-negative disease to determine HPV status of tumor for SCCHN of the oropharynx.³⁹ Note: If results are not available, then a sample (tissue on microscopic slides, tissue block or a fresh tissue biopsy in formalin) should be sent to the central laboratory for analysis and confirmed as shipped.
 - 3. Tumor progression or recurrence within 6 months of last dose of platinum therapy in the adjuvant (ie, with radiation after surgery), primary (ie, with radiation), recurrent, or metastatic setting. Clinical progression after platinum therapy is an allowable event for entry and is defined as progression of a lesion at least 10 mm in size that is amenable to caliper measurement (eg, superficial skin lesion as per RECIST v1.1) or

- a lesion that has been visualized and photographically recorded with measurements and shown to have progressed.
4. Prior curative radiation therapy must have been completed at least 4 weeks prior to study drug administration. Prior focal palliative radiotherapy must have been completed at least 2 weeks before study drug administration.
 5. Subjects must be PD-L1+ on fresh biopsies by IHC testing performed by the central laboratory during the screening period. Refer to [Section 5.7.3.1](#) for the definition of PD-L1+.
- iv. The Signal Detection Cohort Expansion (Part 4 - removed with Revised Protocol 12)
1. Squamous non-small cell lung cancer:
 - a) Subjects with histologically or cytologically documented squamous cell NSCLC who present with Stage IIIB/Stage IV disease (according to version 7 of the International Association for the Study of Lung Cancer Staging Manual in Thoracic Oncology), or with recurrent or PD following multimodal therapy (radiation therapy, surgical resection, or definitive chemoradiation therapy for locally advanced disease).
 - b) Subjects must have experienced disease recurrence or progression during or after 1 prior platinum doublet-based chemotherapy regimen for advanced or metastatic disease.
 - i. Maintenance therapy following platinum doublet-based chemotherapy is not considered as a separate regimen of therapy.
 - ii. Subjects who received platinum-containing adjuvant, neoadjuvant, or definitive chemoradiation therapy given for locally advanced disease, and developed recurrent (local or metastatic) disease within 6 months of completing therapy are eligible.
 - iii. Subjects with recurrent disease > 6 months after platinum-containing adjuvant, neoadjuvant, or definitive chemoradiation therapy given for locally advanced disease, who also subsequently progressed during or after a platinum doublet-based regimen given to treat the recurrence, are eligible.
 - c) Subjects must be PD-L1+ on fresh biopsies by IHC testing performed by the central laboratory during the

screening period. Refer to [Section 5.7.3.1](#) for the definition of PD-L1+.

2. Squamous cell esophageal cancer:

- a) Subjects with histologically confirmed ESCC who must meet all of the following:
 - i. Subjects must have progression or refractory disease. Subjects must have had at least 1 chemotherapy regimen for the treatment of metastatic (Stage IV) or locally advanced disease.

or

 - ii. Subject actively refuses chemotherapy or biological therapy for the treatment of metastatic (Stage IV) or locally advanced disease considered as standard treatment for this disease stage, despite being informed by the investigator about the treatment options. Subjects actively refusing chemotherapy must have had progression or refractory disease prior to starting study drug. The subject's refusal must be thoroughly documented. The investigator will discuss each individual subject refusing chemotherapy with the Sponsor's Medical Monitor to confirm eligibility.

3. Bladder cancer:

[figure not shown]
- a) Histological or cytological evidence of metastatic or surgically unresectable transitional cell carcinoma of the urothelium involving the bladder, urethra, ureter, or renal pelvis. Minor histologic variants (< 50% overall) are acceptable.
 - i. Subjects must have metastatic or surgically unresectable (cT4b, or any N+ [N1-3], or any M-1) disease.
- b) Subjects must have received, and then progressed or been intolerant to, at least 1 standard treatment regimen in the advanced or metastatic setting, if such a therapy exists.

4. Other Squamous Histologies:

- a) Histologic or cytological confirmation of squamous cell carcinoma (excluding SCCHN, sqNSCLC, and ESCC) that is advanced (metastatic, recurrent and/or unresectable) such as, but not limited to, SCC of the skin,

- cervix, vulva, vagina, penis, anorectal and of unknown primary site.
- b) Participants must have received, and then progressed or been intolerant to, at least 1 standard treatment regimen in the advanced or metastatic setting, if such a therapy exists.
 - c) HPV status (except for SCC of the skin) must be documented if known.
5. Subjects with SCCHN who have received prior PD-1/PD-L1 directed therapy:
- a) Histologically confirmed, incurable, locally advanced, recurrent or metastatic SCCHN (oral cavity, pharynx, and larynx), Stage 3/4, and not amenable to local therapy with curative intent (surgery or radiation therapy with or without chemotherapy).
 - b) Documentation of p16-positive or p16-negative disease to determine HPV status of tumor for SCCHN of the oropharynx.³⁹ Note: If results are not available, then a sample (tissue on microscopic slides, tissue block, or a fresh tissue biopsy in formalin) should be sent to the central laboratory for analysis and confirmed as shipped.
 - c) Subjects must have received prior immunotherapy with an anti-PD-1 or anti-PD-L1 containing regimen and must have progressive or recurrent disease after prior PD-1/PD-L1 directed therapy.
 - d) The last dose of prior anti-PD-1/anti-PD-L1 must be ≥ 28 days from initiation of study therapy.
 - e) Prior curative radiation therapy must have been completed at least 4 weeks prior to study drug administration. Prior focal palliative radiotherapy must have been completed ≥ 2 weeks before study drug administration.
 - f) Subjects must be PD-L1+ on fresh biopsies by IHC testing performed by the central laboratory during the screening period. Refer to [Section 5.7.3.1](#) for the definition of PD-L1+.
- v. The Signal Detection in SCCHN with Lirilumab, Nivolumab, and Ipilimumab Combination (Part 5 - enrollment closed)
- 1. Histologically confirmed SCCHN, from any of the following primary sites only: oral cavity, oropharynx, hypopharynx, and larynx [REDACTED].

2. Subjects must have metastatic or recurrent SCCHN that is not amenable to therapy with curative intent (surgery or radiation therapy with or without chemotherapy). Subjects who refuse potentially curative salvage surgery for recurrent disease are ineligible. Subjects must have tumor progression or recurrence after prior platinum-containing systemic therapy for recurrent or metastatic disease. In addition, subjects who have progressed within 6 months of platinum-based therapy used as part of concurrent chemoradiation (definitive or adjuvant therapy) are also eligible.

4. Submission of tumor tissue specimen to the central laboratory for documentation of PD-L1 status by IHC at screening. Subject must have documentation of PD-L1 status by IHC performed by the central lab at randomization. Sample must be from a tumor biopsy collected during screening. Biopsy should be excisional, incisional or core needle. Fine needle aspiration is insufficient.
 5. Prior palliative radiotherapy must have been completed at least 4 weeks prior to first dose of study drug if radiotherapy was to the head and neck region and 2 weeks prior to first dose of study drug if radiotherapy was to other regions.
- vi. The Signal Detection in Previously Untreated MEL with Lirilumab, Nivolumab, and Ipilimumab Combination (Part 6 - removed with Revised Protocol 12)
1. Histologically confirmed unresectable Stage 3 or 4 MEL as per American Joint Committee on Cancer staging system.
 2. Subjects must have known BRAF V600 mutation status or consent to BRAF V600 mutation testing per local institutional standards during the Screening Period.
 3. Treatment-naïve subjects (ie, no prior systemic anticancer therapy for unresectable or metastatic MEL).
 - a) Note: Prior adjuvant or neoadjuvant MEL therapy is permitted if it was completed at least 6 weeks prior to randomization and all related AEs have either returned to baseline or stabilized.

4. Submission of tumor tissue specimen to the central laboratory for documentation of PD-L1 status by IHC at screening. Subject must have documentation of PD-L1 status by IHC performed by the central lab at randomization. Sample must be from a tumor biopsy collected during screening biopsy should be excisional, incisional or core needle. Fine needle aspiration is insufficient.
- b) Presence of at least 1 lesion with measurable disease as defined by RECIST v1.1 criteria for response assessment. Subjects with lesions in a previously irradiated field as the sole site of measurable disease will be permitted to enroll provided the lesion(s) have demonstrated clear progression and can be measured accurately. As of Protocol Amendment 13, subjects undergoing biopsy do not need to have a biopsy lesion that is distinct from an index lesion.
 - c) Subjects must consent to allow the acquisition of existing FFPE material tissue block or tumor tissue sections for performance of correlative studies. In the Dose Escalation and Cohort Expansion (Part 1; completed) and the SCCHN Cohort Expansion (Part 2; completed), for NSCLC, tissue must have been collected within 6 months of study entry. For MEL, tissue must have been collected after prior systemic therapy, if any (these criteria related to the Dose Escalation and Cohort Expansion [Part 1; completed] and the SCCHN Cohort Expansion [Part 2; completed] are not applicable starting with Protocol Amendment 13 and all subsequent amendments).
 - i. In the SCCHN Randomized Cohorts (Part 3) and the Signal Detection in SCCHN with Lirilumab, Nivolumab, and Ipilimumab Combination (Part 5): Subjects must consent to allow the acquisition of existing FFPE material tissue block or tumor tissue sections for performance of correlative studies. **All subjects will be required to provide fresh biopsies at baseline** if a subject has accessible lesions and if the risks associated with obtaining biopsies are deemed acceptable. In addition, all subjects in the SCCHN Randomized Cohorts (Part 3) and the Signal Detection in SCCHN with Lirilumab, Nivolumab, and Ipilimumab Combination (Part 5) will be **required to provide a fresh on-treatment biopsy** if risk is acceptable. Fresh biopsy samples obtained during screening must be submitted to the central laboratory for PD-L1 testing prior to subjects receiving study drug. In the event that the biopsy sample collected during screening is not evaluable for PD-L1, the site will be notified and an archival specimen may be submitted for PD-L1 testing.
 - d) A minimum of 10 subjects each in the MEL cohort and the SCCHN cohort (the Dose Escalation and Cohort Expansion [Part 1; completed]) will be required to undergo mandatory pre-treatment and on-treatment biopsies in the cohort expansion phase at acceptable clinical risk as judged by the investigator. All other subjects will have the option of undergoing pre-treatment, on-treatment, and post-treatment biopsies. The biopsy lesion must be distinct from an index lesion. In the SCCHN Cohort Expansion (Part 2; completed); a minimum of 15 subjects will be required to undergo mandatory pre-treatment and on-treatment biopsies at acceptable clinical risk as judged by the investigator. The biopsy lesion cannot be the sole lesion of measurable disease. Additional subjects may be enrolled in order to satisfy this requirement. These criteria related to the Dose Escalation and Cohort Expansion (Part 1; completed) and the

- SCCHN Cohort Expansion (Part 2; completed) are not applicable starting with Protocol Amendment 13 and all subsequent amendments.
- e) The first dose of study drug must be at least 28 days from the last dose of prior therapy.
 - f) ECOG status of 0 or 1.
 - g) Life expectancy of ≥ 12 weeks.
 - h) Adequate organ function for all subjects except those with HCC as defined by the following:
 - i. White blood cell (WBC) $\geq 2000/\mu\text{L}$
 - ii. Neutrophils $\geq 1500/\mu\text{L}$
 - iii. Platelets $\geq 100 \times 10^3/\mu\text{L}$
 - iv. Hemoglobin ≥ 9.0 g/dL
 - v. Creatinine $\leq 1.5 \times$ upper limit of normal (ULN) or calculated creatinine clearance < 40 mL/min (using the Cockcroft-Gault formula)
 - vi. ALT and AST $\leq 3 \times$ ULN
 - vii. Total bilirubin $\leq 1.5 \times$ ULN (except subjects with Gilbert's Syndrome who must have a total bilirubin level of $< 3.0 \times$ ULN)
 - viii. Normal thyroid function, or have controlled thyroid disorder
 - i) Adequate organ function for all HCC subjects as defined by the following. Not applicable starting with Protocol Amendment 13 and all subsequent amendments.
 - i. WBC $\geq 2000/\mu\text{L}$ (stable off any growth factor within 4 weeks of first study drug administration)
 - ii. Neutrophils $\geq 1000/\mu\text{L}$ (stable off any growth factor within 4 weeks of first study drug administration)
 - iii. Platelets $\geq 40 \times 10^3/\mu\text{L}$ (transfusion to achieve this level is not permitted within 2 weeks of first study drug administration)
 - iv. Hemoglobin ≥ 8.5 g/dL (transfusion to achieve this level is not permitted within 2 weeks of first study drug administration)
 - v. Creatinine $\leq 1.5 \times$ ULN
 - vi. ALT and AST $\leq 5 \times$ ULN
 - vii. Total bilirubin ≤ 3 mg/dL
 - viii. International normalized ratio ≤ 2.3 or prothrombin time ≤ 6 sec above control
 - ix. Albumin ≥ 2.8 g/dL
 - x. Normal thyroid function, or have controlled thyroid disorder
 - j) Ability to comply with treatment, PK and pharmacodynamics sample collection and required study follow-up.

- k) Subject re-enrollment: this study permits the re-enrollment of a subject who has discontinued the study as a pre-treatment failure (ie, subject has not been randomized/has not been treated). If re-enrolled, the subject must be re-consented.
- l) Subjects with interstitial lung disease that is symptomatic or may interfere with the detection or management of suspected drug-related pulmonary toxicity
- m) Subjects must have resting baseline oxygen saturation measured by pulse oximetry of $\geq 92\%$ at rest on room air.

3) Age, Sex, and Reproductive Status

- a) Men and women, ages ≥ 18 years.
- b) Women of childbearing potential (WOCBP) must have a negative serum or urine pregnancy test (minimum sensitivity 25 IU/L or equivalent units of human chorionic gonadotropin) within 24 hours prior to the start of study drug.
- c) Women must not be breastfeeding.
- d) WOCBP must agree to follow instructions for method(s) of contraception for the duration of study treatment with nivolumab and 5 months after the last dose of study drug (ie, 30 days [duration of ovulatory cycle] plus the time required for the study drug to undergo approximately 5 half-lives.)
- e) Males who are sexually active with WOCBP must agree to follow instructions for method(s) of contraception for the duration of study treatment with nivolumab and 7 months after the last dose of study drug (ie, 90 days [duration of sperm turnover] plus the time required for the study drug to undergo approximately 5 half-lives.)
- f) Azoospermic males and WOCBP who are continuously not heterosexually active are exempt from contraceptive requirements; however, they must still undergo pregnancy testing as described in this section.

Investigators shall counsel WOCBP and male subjects who are sexually active with WOCBP on the importance of pregnancy prevention and the implications of an unexpected pregnancy. Investigators shall advise WOCBP and male subjects who are sexually active with WOCBP on the use of highly effective methods of contraception (see [Appendix 6](#)).

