- Enrollment permanently closed in Part 3, a single-blinded, placebo-controlled, randomized cohort expansion of lirilumab in combination with nivolumab vs nivolumab monotherapy in subjects with platinum-refractory recurrent or metastatic SCCHN who are PD-L1+.
- Removal of Part 4, a signal detection cohort expansion of nivolumab and lirilumab at a flat dose in subjects with sqNSCLC, ESCC, BC, and other squamous histologies and in subjects with SCCHN who have received prior PD-1/PD-L1 directed therapy. No subjects were enrolled.
- Enrollment permanently closed in Part 5, a safety and signal detection with a triplet regimen of lirilumab in combination with nivolumab and ipilimumab in subjects with platinum-refractory recurrent or metastatic SCCHN.

- Removal of Part 6, a safety and signal detection with a triplet regimen of lirilumab in combination with nivolumab and ipilimumab in subjects with previously untreated metastatic melanoma. No subjects were enrolled.
- Removal of overall survival visits for all subjects, select sample collection and study visits, additional subjects entering treatment beyond progression and retreatment at the time of disease progression.
- All subjects will be permitted a maximum of up to 2 years of treatment as specified in the individual study parts.

Background of NK Cells and KIR in Inflamed Tumors

An analysis of the immune infiltration in a large cohort of head and neck tumors, integrating genetic data with RNA-seq-based deconvolution of immune cell populations and effector/regulatory molecules was done³ and found that SCCHN is one of the most highly immune-infiltrated cancer types, and in fact, the most highly NK cell- and Treg-infiltrated cancer type. These tumors are poised to benefit from immunotherapy that includes Treg and NK checkpoint-targeted approaches that may have unique applicability in head and neck cancer.

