3.5 Discontinuation of Subjects from Treatment

Subjects MUST discontinue investigational product (and non-investigational product at the discretion of the investigator) for any of the following reasons:

- Withdrawal of informed consent (subject's decision to withdraw for any reason)
- Any clinical AE, laboratory abnormality, clinical deterioration, or concurrent illness that in the opinion of the investigator indicates that continued participation in the study is not in the best interest of the subject
- Pregnancy
- Termination of the study by BMS
- Loss of ability to freely provide consent through imprisonment or involuntary incarceration for treatment of either a psychiatric or physical (eg, infectious disease) illness

- Documented and confirmed irPD as defined by irRECIST for the Dose Escalation and Cohort Expansion (Part 1; completed) and the SCCHN Cohort Expansion (Part 2; completed) (see [Appendix 2](#)).
- Documented PD for the SCCHN Randomized Cohorts (Part 3), and the Signal Detection in SCCHN with Lirilumab, Nivolumab, and Ipilimumab Combination (Part 5) as defined by RECIST v1.1 (see [Appendix 3](#)).
- Documented and confirmed irCR as defined by irRECIST for the Dose Escalation and Cohort Expansion (Part 1; completed) and the SCCHN Cohort Expansion (Part 2; completed) (see [Appendix 2](#)).
- Documented and confirmed CR for the Signal Detection in SCCHN with Lirilumab, Nivolumab, and Ipilimumab Combination (Part 5) as defined by RECIST v1.1 (see [Appendix 3](#)).
- Discretion of the investigator
- Inability to comply with the protocol requirements
- Protocol defined reasons for discontinuation (see [Section 4.9.5](#))
- Maximum treatment duration of up to a maximum of 2 years; 12 cycles in Parts 1, 2, and 3 or 8 cycles in Part 5.

In the case of pregnancy, the investigator must immediately notify the Sponsor or designee of this event. In most cases, the study drug will be permanently discontinued in an appropriate manner (eg, dose tapering if necessary for subject safety). Please contact the Sponsor or designee within 24 hours of awareness of the pregnancy. If the investigator determines a possible favorable benefit/risk ratio that warrants continuation of study drug, a discussion between the investigator and the Sponsor or designee must occur.

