4.9.4 Criteria for Subsequent Dosing

Subsequent dosing may continue if subjects continue to meet laboratory criteria as listed in [Section 3.3.1](#). The investigator will determine if subsequent dosing is appropriate for subjects who have laboratory or clinical abnormalities that do not meet DLT (Section 4.8) or discontinuation criteria (Section 4.9.5). All related Grade 2 toxicities should be discussed with the BMS Medical Monitor prior to subsequent dosing.

Subjects may resume treatment with study drug when the drug-related AE(s) resolve to Grade ≤ 1 or baseline value, with the following exceptions:

- Subjects may resume treatment in the presence of Grade 2 fatigue.
- Subjects who have not experienced a Grade 3 drug-related skin AE may resume treatment in the presence of Grade 2 skin toxicity.
- For subjects with Grade 2 AST, ALT, and/or total bilirubin abnormalities, dosing may resume when laboratory values return to baseline and management with corticosteroids, if needed, is complete.
- Subjects with combined Grade 2 AST/ALT and total bilirubin values meeting discontinuation parameters (Section 4.8) should have treatment permanently discontinued.
- Drug-related pulmonary toxicity, diarrhea, or colitis must have resolved to baseline before treatment is resumed. Subjects with persistent Grade 1 pneumonitis after completion of a steroid taper over at least 1 month may be eligible for retreatment if discussed with and approved by the BMS Medical Monitor.

- Subjects with drug-related endocrinopathies adequately controlled with only physiologic hormone replacement may resume treatment after consultation with the BMS Medical Monitor. Adrenal insufficiency requires discontinuation regardless of control with hormone replacement.

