BSA = body surface area; BUN = blood urea nitrogen; Ca = calcium; CBC = complete blood count; Cl = chloride; CRP = C-reactive protein; D = Day; ECG = electrocardiogram; K = potassium; LDH = lactate dehydrogenase; LFT = liver function test; Mg = magnesium; Na = sodium; PE = physical examination; T3 = triiodothyronine; T4 = thyroxine; TAO = Trial Access Online; TSH = thyroid-stimulating hormone.

Table 5.1.2-2: On-treatment Procedural Outline the SCCHN Randomized Cohorts (Part 3 - closed to enrollment) (CA223001)

Procedure	8-week Cycle, until PD					Notes
	D1 (± 2 days)	D15 (± 2 days)	D29 (± 2 days)	D43 (± 2 days)	D49 to 56	
Safety Assessments						
Physical Examination	X					A symptom directed physical examination performed by the investigator or designee is required at each subsequent visit.
Performance Status	X	X	X	X		ECOG score (see Appendix 7)
Physical Measurements	X	X	X	X		Weight only.
Vital Signs	X	X	X	X		Includes body temperature, seated blood pressure, and heart rate. Blood pressure and heart rate should be measured after the subject has been seated quietly for at least 5 minutes. Vital signs will be obtained before the nivolumab infusion, after the nivolumab infusion, and after the lirilumab or placebo for lirilumab infusion.
Electrocardiogram	X					12-lead ECG (if performed on same day as study drug administration it is to be performed prior to dosing). Not required on Cycle 1 Day 1
Chest Radiograph						As clinically indicated.
Oxygen Saturation Levels	X	X	X	X		Collected at rest and after mild to moderate exertion prior to dosing.
Laboratory Tests	X	X	X	X		On-study laboratory tests (including pregnancy testing) to be done on site/local. Within 72 hours of re-dosing to include CBC with differential, LFTs (to include a minimum of AST, ALT, alkaline phosphatase, total bilirubin, and LDH), BUN, creatinine, glucose, Ca, Mg, Na, K, carbon dioxide, Cl, phosphorous, amylase, lipase, and troponin. Results should be examined by the investigator or appropriate designee prior to dose administration.

Table 5.1.2-2: On-treatment Procedural Outline the SCCHN Randomized Cohorts (Part 3 - closed to enrollment) (CA223001)

Procedure	8-week Cycle, until PD					Notes
	D1 (± 2 days)	D15 (± 2 days)	D29 (± 2 days)	D43 (± 2 days)	D49 to 56	
Endocrine Panel	X					To include TSH with reflex testing (free T3 and free T4). Results should be examined by the investigator or appropriate designee within 48 hours of dose administration.

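### Inclusion item 2h(v) has its inequality reversed: above 1.5 × ULN creatinine, a clearance below 40 mL/min counts as adequate renal function and 40 or more does not

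*Protocol*

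**What the plan says.** Item 2h of Protocol Section 3.3.1 opens "Adequate organ function for all subjects except those with HCC as defined by the following". Sub-item (v) offers two ways to qualify, joined by *or*: creatinine no higher than 1.5 × ULN, or "calculated creatinine clearance < 40 mL/min" by Cockcroft-Gault. The parallel renal line for HCC subjects, item 2i(v), has the creatinine ceiling only. Item 2i is marked not applicable from Amendment 13. Item 2h carries no such note, so it is current text.

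The criteria must "be met prior to dosing on Day 1" (Section 3.3), with no exceptions allowed. Entry is now over: Section 1 records "Enrollment permanently closed in Part 3" and says the same of Part 5, while Parts 1 and 2 had already completed enrollment.

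The laboratory criteria live on in Section 4.9.4: "Subsequent dosing may continue if subjects continue to meet laboratory criteria as listed in" Section 3.3.1. That section goes on: "The investigator will determine if subsequent dosing is appropriate for subjects who have laboratory or clinical abnormalities that do not meet DLT" or discontinuation criteria.

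**The concern.** Higher creatinine clearance means better kidney function. An alternative limb introduced by *or* normally rescues a subject whose serum creatinine is high but whose calculated clearance is still acceptable. Here it rescues only subjects whose clearance is poor. The other items in the list where higher is better (white cells, neutrophils, platelets, hemoglobin) are all lower bounds; the clearance limb is the one that runs the other way.

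What is at stake is safety wording, not inference. Subjects still deriving benefit may stay on treatment under Revised Protocol 12. A site that applies Section 4.9.4 literally would read a subject with raised creatinine and clearance below 40 mL/min as meeting the renal criterion for further dosing.

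**Working it through.** **Logic of the item as written.** It is met if creatinine ≤ 1.5 × ULN or clearance < 40 mL/min.

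| Creatinine | Clearance (mL/min) | As written | With ≥ 40 |
|---|---|---|---|
| ≤ 1.5 × ULN | ≥ 40 | met | met |
| ≤ 1.5 × ULN | < 40 | met | met |
| > 1.5 × ULN | ≥ 40 | **not met** | met |
| > 1.5 × ULN | < 40 | **met** | not met |

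Only the last two rows change, so only non-HCC subjects above 1.5 × ULN are affected.

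**Size in clinical terms.** The plan states no figure to reproduce. The documents give no weight or creatinine data for SCCHN subjects, so sex, age, weight and ULN below are all assumptions.

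- Cockcroft-Gault: CrCl = (140 − age) × weight / (72 × Scr), times 0.85 for women.
- Creatinine at which CrCl = 40: Scr40 = (140 − age) × weight / 2880, times 0.85 for women.
- Above 1.5 × ULN the item as written fails only when 1.5 × ULN < Scr ≤ Scr40. If Scr40 ≤ 1.5 × ULN, no creatinine value fails it.

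Age 60, ULN 1.2 mg/dL, so 1.5 × ULN = 1.8 mg/dL:

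| Weight (kg) | Scr40, man | Range failing as written | Scr40, woman | Range failing as written |
|---|---|---|---|---|
| 50 | 1.39 | none | 1.18 | none |
| 60 | 1.67 | none | 1.42 | none |
| 70 | 1.94 | 1.80–1.94 | 1.65 | none |
| 80 | 2.22 | 1.80–2.22 | 1.89 | 1.80–1.89 |
| 90 | 2.50 | 1.80–2.50 | 2.12 | 1.80–2.12 |

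The same man at creatinine 2.0 mg/dL has CrCl = 80 × weight / 144:

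- 80 kg: 44.4, fails
- 70 kg: 38.9, meets
- 60 kg: 33.3, meets

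**Wider grid.** Both sexes; 50, 60, 70, 80, 90 kg; ages 50, 60, 70; ULN 1.0, 1.2, 1.4 mg/dL: 2 × 5 × 3 × 3 = 90 combinations.

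| Creatinine (mg/dL) | Combinations above 1.5 × ULN | Met as written (CrCl < 40) | Failed as written (CrCl ≥ 40) |
|---|---|---|---|
| 2.0 | 60 | 42 | 18 |
| 2.5 | 90 | 81 | 9 |
| 3.0 | 90 | 90 | 0 |

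At 3.0 mg/dL clearance runs from 13.8 (woman, 70 years, 50 kg) to 37.5 mL/min (man, 50 years, 90 kg). With ≥ 40, none of the 90 would meet the item. The opposite error, failing despite clearance of 40 or more, is possible at some creatinine value in 45 of the 90 combinations (27 of 45 male, 18 of 45 female).

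**Whether the limb would be applied.** The on-treatment laboratory rows (Tables 5.1.1-2, 5.1.2-2 and 5.1.4-2) list serum creatinine but not calculated clearance. In Part 3, for example, the chemistry items run "BUN, creatinine, glucose, Ca, Mg, Na, K, carbon dioxide, Cl, phosphorous, amylase, lipase, and troponin". No section requires clearance to be computed before a dose.

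**What else stops dosing.** Section 3.5 makes discontinuation mandatory for "Any clinical AE, laboratory abnormality, clinical deterioration, or concurrent illness that in the opinion of the investigator indicates" that continuing is not in the subject's best interest. Section 4.9.3 (last bullet) and Section 4.9.5 (item 7) add delay and discontinuation on investigator judgement. None of these three depends on the event being drug-related.

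**The case against.** The strongest case against is that the practical effect is close to nil.

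- **Drug-related renal decline is covered elsewhere.** Section 4.9.3 delays dosing for Grade 2 drug-related creatinine abnormalities. Section 4.9.4 requires drug-related events to settle to Grade 1 or baseline first, and Section 4.9.5 (item 4) stops treatment for Grade 4 drug-related creatinine. These apply whatever item 2h(v) says. This stands, and it leaves mainly non-drug-related rises, where the investigator-judgement stops apply.
- **Entry had other barriers.** Section 3.3.2 excludes serious or uncontrolled medical disorders and any Grade 4 laboratory abnormality. True, but neither sets a renal threshold or corrects the sign.
- **The grid is assumed.** At 3.0 mg/dL every clearance in it is below 40, so the 90-of-90 result follows from choosing that value. That is fair: the grid shows how the item behaves and says nothing about how many trial subjects it touches.
- **It is one symbol, appearing once.** The SAP does not repeat item 2h, so there is no second statement to check it against, and a character error in the electronic text cannot be wholly excluded. The neighbouring inequalities read sensibly, so this is a reason to check the source, not to drop the point.
- **The intended limit is unknown.** A limit of > 40, or deleting the limb to match item 2i(v), would also be coherent. This stands and shapes the fix.

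None of this makes the wording right.

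**Conclusion.** The concern holds as a minor one. The direction of the inequality is wrong, it is current text, and no section of either document corrects it. The error itself follows from the wording and needs no assumption beyond the symbol having been reproduced faithfully. Its reach is narrow: non-HCC subjects still on treatment with creatinine above 1.5 × ULN, at a site that applies the clearance limb literally under Section 4.9.4. Meeting the limb does not compel a dose and failing it does not bar one. How many such subjects exist is not stated and may be none. Response rates, sample sizes, error rates and every SAP analysis are untouched.

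**What to change.** In the next protocol revision, change the clearance limb of item 2h(v) from < 40 to ≥ 40 mL/min, after the sponsor's clinical team has checked the source text and confirmed the intended limit. Section 9.1.1 requires IRB/IEC review for the revision. An administrative letter, of which investigators must inform their IRB/IEC, can warn sites in the interim.

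The cost is one symbol in a revision, plus the optional letter. The SAP needs no change: its programmable deviation list (Section 7.2.3) has no renal item.
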